#### **Quantitative Analysis**

We will conduct descriptive analyses and multivariate modeling of data to examine changes in outcomes over time and explore moderating variables. All analyses will be intent to treat and conducted as described in our analytic plan and associated protocol. If diagnostic or sensitivity analyses dictate changes to those plans, we will clearly identify subsequent analyses as ad hoc or otherwise deviating from an a priori plan, including labeling subgroup and interaction analyses as confirmatory, exploratory, or post hoc. Our statistician will remain masked to study arm to reduce bias.

Prior to hypothesis testing for Aims 1 and 2, data will be explored by descriptive data analysis. Summary statistics including means, standard deviations, medians, and ranges for continuous variables, or frequencies and percentages for categorical variables, will be presented for the entire sample and stratified by approach at each time point. We will assess the balance of key covariates by visually assessing the standardized differences. We will conduct baseline data analysis for each outcome to explore any pre-intervention differences in outcomes between TEAM and TECH at baseline. Two-sided Wald T-test or Wald F-test using the generalized linear mixed models (GLMMs) with normally distributed random effects for three sites will be used. This estimating method using GLMMs will produce consistent estimations of the regression parameters under the missing at random (MAR) or missing completely at random (MCAR) mechanism. The MAR assumption will be verified in the sensitivity analysis (see handling missing data in quantitative analyses). Distributions of outcomes and key covariates over time will also be visually examined to identify systematic departures from normality and overall pattern over time, assisting us in evaluating the distribution of data and determining if assumptions are met for subsequent modeling approaches. We will conduct statistical analysis on transformed outcomes using Box Cox- or log-transformation to address any asymmetry.

Aim 1 will examine the impact of TEAM vs. TECH on the primary and secondary outcomes and will determine if changes in outcomes over time are different between the two groups. We will fit the GLMMs to associate each outcome with the intervention (TEAM vs. TECH) and other covariates of interest. To account for the within-patient correlation in longitudinal data and to reflect potential differences among three sites, we will add normally distributed random effects for patients and sites in addition to the fixed effects for intervention and covariates of interest. An inference of the intervention effects for each outcome will be carried out using Wald test based on the either F-distribution or Chi-square distribution as appropriate. For each outcome, the null hypothesis of homogeneous change in outcomes overtime between TEAM and TECH will be examined by testing the treatment-by-time interaction effect on each outcome. In the absence of significant interaction effects, the marginal difference in outcomes between TEAM and TECH will be examined using the same GLMMs without the interaction effect. All hypothesis tests for Aim 1 will be conducted at the overall significance level of 0.05. The score changes from baseline to each time point and their difference between TEAM and TECH will be estimated with 95% confidence intervals.

Given our study Aim 2 to understand how TEAM and TECH provide different benefits to individuals with different characteristics, we will explore potential heterogeneity of treatment effects in clinical response between subgroups of patients defined using patients' baseline characteristics. All co-variates will be identified a-priori. For Aim 2.a, we will examine whether and how the effect of TEAM and TECH approaches on BH symptom severity varies between patients with a high level of IBD disease activity (HBI or UCAI score > 4) and patients with low disease activity (HBI or UCAI score <=4) at baseline. IBD disease activity and effect of TEAM and TECH approach will also be assessed using a recently developed, validated, and preferred measure of disease activity for Crohn's disease and UC (PRO-2). 63,64 For statistical inference, we will fit the same GLMMs as described in Aim 1 and will include the higher order interaction terms with subgroups of patients defined by IBD activity. The null hypothesis of homogenous treatment effect between patients with high and low IBD activity in each outcome will be examined via interaction analysis (three-way interaction of time, treatment, and subgroup of IBD severity; two-way interaction of treatment and subgroup of IBD severity in the absence of a significant three-way interaction effect) using Wald test based on either F-distribution or Chisquare distribution as appropriate at the significance level of 0.05. In the presence of statistically significant treatment heterogeneity, the score change in BH symptom severity from baseline to each time point and their difference between TEAM and TECH will be estimated with 95% confidence intervals for subgroup of patients defined by IBD severity. For Aim 2.b, we will explore whether and how the effect of TEAM and TECH approaches on primary outcomes varies between young (age<=30) and older (age>30) patients. We will also examine the impact of TEAM and TECH on patients with differing IBD diagnoses, namely ulcerative colitis and Crohn's disease. Further, we will explore the effect of site differences, behavioral health history, insurance type (public vs. not), e-health literacy, and medications on response to TEAM or TECH intervention as secondary and exploratory analyses. For statistical inference, the same hypothesis test and statistical model described in Aim 2.a will be used. We will make a Bonferroni correction for multiple testing in order to conduct subgroup analyses at the overall significance level of 0.05. In the presence of statistically significant treatment heterogeneity,

estimation of score changes in each outcome and their difference between TEAM and TECH will be presented with 95% confidence intervals for each subgroup of patients.

In handling missing data in quantitative analyses, we will attempt to determine the reasons for missing data and dropouts. The MAR assumption will be examined by comparing baseline characteristics between participants with and without missing data and conducting sensitivity analysis by repeating the main analyses without participants with missing data. If we observe statistical evidence that data are not MAR, we will stratify the participants into subgroups that share the same missing data pattern and estimate the statistical model separately for each missing data pattern. The results of all missing data analyses will be presented, and the sensitivity of our inference to the assumptions and approaches will be included in the interpretation of results.

COVID Considerations for Aims 1-2: Of our 675 projected participants, 32 were enrolled and completed their 6-month/primary outcomes surveys before the beginning of the COVID-19 (i.e., prior to March 12, 2020); 211 are potentially COVID-confounded (i.e., enrolled prior to or during the acute phase of the pandemic and were followed during it), and 432 were enrolled in the post-COVID phase of the study (after June 2021). Primary analyses will focus on the full sample of N=675, controlling for whether the participant was COVID-confounded. In sensitivity analyses, we will include only participants enrolled during the post-COVID phase. Effect sizes from sensitivity analyses will be assessed to evaluate whether findings are similar to those from the primary analyses.

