Aim 1: We calculated statistical power for the target sample size of 675, with approximately 337 participants enrolled into both TEAM and TECH. After adjusting for the multiple testing in Aim 1 (2 tests) and considering 25% attrition, a sample size of 505 (approximately 252 per treatment group) will provide over 99.9% power for the hypothesis test for Aim 1. Among patients enrolled in the specialty medical home at that time who met active behavioral criteria (PHQ-4 >= 6), there was a significantly greater change in TECH (n=73; ES .49) versus TEAM (n=106; ES .36) for the behavioral composite but both approaches were associated with significant change over time (p=.005). Both approaches were also associated with significant improvement in the biological composite for both TEAM (ES .22) and TECH (ES .16). With the IBD SMH models of care being clinically operational at all three sites, we are collecting ongoing useful and robust information that has been published. In our most recent analyses of our clinical research registry tracking our TEAM approach (n=280), our most recent analyses show effect sizes comparable to these initial findings for both approaches.

Aim 2: We considered both subgroup analyses and formal tests of moderation. Subgroup analyses – Based on current data, our subgroups are relatively evenly proportioned. We expect that the smallest subgroup will be 42% of the sample and the largest will be 58% of the sample. Thus, our expected subgroup sizes after 25% attrition are between 212 and 293 for projected enrollment. For this range of subgroup Ns, we expect 0.80 power to detect small treatment effects ranging between 0.26 and 0.30. Moderation – We used Monte Carlo methods (100 runs) to simulate the binary moderator (M) and treatment (X) (both p=0.5), assuming M independent of X as expected in a randomized trial. Considering a range of effect sizes for B1, B2, and B3, we estimated the outcome Y as Y=B1\*X+B2\*M+B3\*X\*M+ $\varepsilon$ , where  $\varepsilon$ ^N(0,1). We averaged across

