scenarios to determine the typical effect of B3 that can be detected with our current and projected sample sizes after 25% attrition. B3 can be interpreted as the difference between the treatment effect size among those with M=0 (D0=B1). With our projected sample sizes (N=505 after 25% attrition), we expect 0.80 power to detect a significant interaction when the magnitude of B3 is at least 0.50. To provide context for these effect sizes, we note that a B3 of 0.50 could correspond, for example, to a moderate effect of X in one subgroup (e.g., D1=0.60) and a small effect of X in the other subgroup (e.g., D0=0.10).

Our sample size calculations are consistent with the literature for both TEAM and TECH for behavioral and physical disease severity outcomes and there is literature supporting engagement and better outcomes with TECH approach with the younger cohort and those with higher eHealth-literacy. However, the research proposed will be beneficial even if we do not prove our hypotheses. For example, even if TEAM and TECH do not differ in Aim 1, the results can still suggest that TECH is feasible and allows TEAM to be utilized more efficiently. In Aim 2, even if we do not show a strong differential impact of the interventions based on IBD activity, we will still learn valuable information about which subgroups of behaviorally complex IBD patients have highest engagement and impact with each approach.

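### The MAR consistency statement omits a condition: without covariate-by-time terms in the Aim 1 model, dropout related to a baseline trait can bias the TEAM–TECH change contrast even when MAR holds

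*Combined protocol and SAP*

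**What the plan says.** All references are to the combined protocol and SAP.

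- **Quantitative Analysis, general paragraphs.** "This estimating method using GLMMs will produce consistent estimations of the regression parameters under the missing at random (MAR"), or missing completely at random. No condition on the mean model is attached.
- **Quantitative Analysis, Aim 1.** The model has random effects for patients and sites "in addition to the fixed effects for intervention and covariates of interest". The one interaction stated is treatment by time. The Measures section lists candidate covariates, and the COVID paragraph adds an indicator for COVID-confounded participants. The plan does not say which other covariates enter the Aim 1 model, or in what form.
- **Quantitative Analysis, Aim 2.** Time-by-treatment-by-subgroup terms are added to test heterogeneity by IBD activity, age and diagnosis. Nothing carries them back into the Aim 1 contrast.
- **Handling of missing data.** MAR is examined by "comparing baseline characteristics between participants with and without missing data", with no mention of arm, and by a rerun without participants who have missing data. If the data appear not to be MAR, separate models are fitted for each missing-data pattern.
- **Aims, and Sample Size and Power Calculations.** Hypotheses 2a and 2b expect response to differ by IBD activity and age. The power section adds that "there is literature supporting engagement and better outcomes with TECH approach with the younger cohort". It also assumes 25% attrition.

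**The concern.** Under MAR, a likelihood-based mixed model is consistent only if its mean structure is right for the variables that govern missingness. A covariate entered as a plain main effect shifts every visit by the same amount, so it does not adjust change from baseline. With complete data this does no harm, because randomization balances the trait. With dropout, the retained patients in each arm can differ in trait mix. If the trait also affects how much patients change, the treatment-by-time contrast absorbs part of that difference, although missingness depends only on an observed baseline variable.

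This matters in a comparison of high-touch and low-touch care, where different kinds of patients may stop supplying data. At stake are a stated property that the model as described does not guarantee, and two safeguards that may not reveal or repair the problem.

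**Working it through.** **Inputs from the plan.** The target is 675 participants, about 337 per arm, reduced for dropout as follows: "After adjusting for the multiple testing in Aim 1 (2 tests) and considering 25% attrition, a sample size of 505". Tests are two-sided, and "All hypothesis tests for Aim 1 will be conducted at the overall significance level of 0.05". The plan's moderation example uses a moderator at 50%, residual SD 1 and an interaction B3 = 0.50. Outcome surveys are at baseline, 6 and 12 months. The earlier behavioral effect sizes were 0.49 (TECH) and 0.36 (TEAM), a gap of 0.13.

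**The plan's own figures reproduce.** 675 × 0.75 = 506 (stated 505). With two balanced binary factors, SE(B3) = 4/√505 = 0.178, so power = Φ(0.50/0.178 − 1.96) = 0.80, as stated.

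**Assumptions not in the documents.** One binary trait at 50%; within-patient correlation 0.5; no site variance; dropouts have baseline data only; overall dropout 25%, depending only on arm and trait (hence MAR).

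**Retained-share formula.** With equal trait groups and dropout d1 (trait present) and d0 (absent), the retained trait share is s = (1 − d1)/[(1 − d1) + (1 − d0)]. If g is the trait's effect on change in an arm, completers give

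bias = (s_TECH − 0.5)·g_TECH − (s_TEAM − 0.5)·g_TEAM.

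Example: TECH loses 35% with the trait and 15% without, TEAM the reverse, g = 0.5 in both arms. Then s_TECH = 0.65/1.50 = 0.433, s_TEAM = 0.85/1.50 = 0.567, and bias = −0.067 × 0.5 − 0.067 × 0.5 = −0.067 SD.

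**Simulation of the 12-month change contrast** (1,500 trials of 675, random-intercept likelihood model, half the change reached by 6 months). The plan's model has arm, time, arm by time and the trait as a main effect. The amended model adds the centred trait by time and by arm.

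| Scenario | Formula | Plan's model: bias | 5% test rejects the true value | Complete-case bias | Amended model: bias; rejects |
|---|---|---|---|---|---|
| Mirrored 10/40%, trait affects level only | 0 | 0.000 | 0.061 | 0.000 | 0.000; 0.059 |
| Mirrored 15/35%, g = 0.5 both arms | −0.067 | −0.053 | 0.093 | −0.067 | −0.001; 0.048 |
| Mirrored 10/40%, g = 0.5 both arms | −0.100 | −0.081 | 0.165 | −0.102 | −0.002; 0.051 |
| Mirrored 10/40%, B3 = 0.50 in TECH only | −0.050 | −0.043 | 0.085 | −0.053 | −0.004; 0.055 |
| Mirrored 10/40%, crossing ±0.25 | 0 | −0.001 | 0.057 | −0.001 | −0.001; 0.056 |
| Same 10/40% in both arms, g = 0.5 both | 0 | +0.001 | 0.073 | 0.000 | +0.001; 0.063 |
| Same 10/40% in both arms, B3 = 0.50 in TECH only | −0.050 | −0.053 | 0.102 | −0.054 | −0.005; 0.058 |

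The SE of the contrast is about 0.087. The Monte Carlo error of a 5% rejection rate is √(0.05 × 0.95/1500) ≈ 0.006. The last row shows that dropout need not differ by arm. The crossing row cancels only because dropout is mirrored: with the same dropout in both arms the formula gives (−0.1)(−0.25) − (−0.1)(0.25) = 0.05.

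**Milder cases, 6-month contrast** (4,000 trials, 337 per arm, no true average effect, 20-point gaps).
- Mirrored dropout, age groups differing by 0.3 to 0.5 SD in change: bias 0.031 to 0.049 SD, 5% test rejects 7.1% to 10.0%.
- Retention and response depend on age in TECH only: bias 0.018 to 0.030 SD, rejects 5.4% to 6.1%.
- With the added terms: bias at most 0.0025 SD, rejects 4.8% to 5.2%.

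**What the missingness comparison sees.**
- *Mirrored dropout:* each trait group loses 25% overall, so a comparison pooled over arms has nothing to find. It flagged the trait in 3% to 4% of trials; a check within arms flagged it in at least 99.9%.
- *TECH-only dropout (15/35% against 25/25% in TEAM):* the pooled rates are 20% and 30%. The difference of 0.10 has SE √[(0.20 × 0.80 + 0.30 × 0.70)/337] = 0.033, so z = 3.0 and power ≈ 0.85. Simulation gave about the same.

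**What the fallback does.** In these scenarios a separate model per missing-data pattern gives no estimate of change for baseline-only patients, and for completers it repeats the complete-case analysis. The trait's effect on change never enters the model.

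**The case against.** Several stronger readings are tempting, and the documents do not support them.

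- *The plan excludes interactions.* It does not. The Aim 1 sentence on fixed effects omits even time, so it is not an exhaustive list of terms. Covariate-by-time terms are unstated, not ruled out, and Aim 2 fits such terms for the same three factors. What stands is that no such term is stated for Aim 1 and the Aim 2 results are not averaged back.
- *The plan predicts differential dropout.* The power section speaks of engagement with TECH. The Measures section assesses engagement through usage and visit data, not survey completion, and under intention to treat a disengaged participant can still supply outcomes. The plan does expect differing response; it gives no dropout by arm or trait.
- *The estimate will be biased.* Not necessarily: bias is nil when the trait affects level only, or when shifts cancel.
- *The check is blind.* That is true only for mirrored dropout, and only if the comparison is pooled over arms, which is inferred from silence. One-arm dropout is usually detected. Descriptive summaries by arm at each visit may also show a shift, though they do not test dropout by trait within arm.

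The size also leans toward the unfavourable end. If half of the dropouts leave after the 6-month visit, the 6-month bias in the mirrored 15/35% case (0.5 SD difference) falls from 0.052 to 0.023 SD and rejection from 10% to about 7%; the 12-month bias falls only to 0.041. At 0.025 per test, one way to split alpha over the two Aim 1 tests, the 12-month mirrored 15/35% case rejects 5.5%. Finally, the near-zero bias after the fix is partly by construction, since the simulated driver of dropout is the variable added.

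**Conclusion.** The point holds as a conditional one. The consistency statement is broader than the Aim 1 model as described can support. If a baseline trait drives both dropout and change, the contrast can be biased under MAR, and the complete-case rerun shares that bias.

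Under assumed 20-point dropout gaps by trait, the bias is about 0.02 to 0.05 SD, with false-positive rates of about 5% to 10%. For scale, 0.05 SD is about 0.05/0.087 = 0.6 of a standard error and 0.05/0.13 = 38% of the earlier gap between TECH and TEAM. With 30-point gaps it reaches 0.08 SD in the mixed model and 0.10 in complete cases. These sizes rest on the assumed dropout pattern, correlation of 0.5, one balanced trait and mostly early dropout. This is a cheap improvement to the plan; bias in this trial has not been shown.

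**What to change.** 1. **Aim 1 model.** Pre-specify the stratification factors (age group, IBD activity, IBD type) and, if wanted, baseline eHealth literacy as covariates, with covariate-by-time and covariate-by-arm-by-time terms. Centre each at the mean of all randomized participants, so that arm by time estimates the effect in the randomized sample. Use any other trait found to predict missingness only in a labelled sensitivity analysis; selecting terms for the primary model from the data would conflict with the plan's rule that covariates are identified in advance.
2. **Missing-data paragraph.** Report missingness by arm and test the arm-by-characteristic interaction on missingness.
3. **Consistency sentence.** Limit it to missingness that depends on observed outcomes and on covariates whose effect on change is in the model.

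The cost is SAP wording and a few terms on variables already collected. For one balanced trait no precision was lost (empirical SE 0.087 with the terms, 0.090 without, in the mirrored 15/35% case with a 0.5 SD difference). For three or four covariates a small loss is to be expected; that was not simulated.

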## **Inclusion/Exclusion Criteria**

#### **Inclusion Criteria**

Individuals who (1) are age 18-60; (2) have a diagnosis of Crohn's or UC; (3) have mild-to-severe behavioral health symptoms, defined as >=6 on either depressive or anxiety severity scales (PHQ-4); (4) consent to be randomized; (5) must have a smartphone; and (6) speak English.

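### The covariance of repeated measures rests on patient random effects alone; read as a random intercept, this leaves the visit-specific 95% confidence intervals for continuous outcomes miscalibrated unless variances and correlations are equal across visits

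*Combined protocol and SAP*

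**What the plan says.** Under Quantitative Analysis, the Aim 1 paragraph fits generalized linear mixed models in which "we will add normally distributed random effects for patients and sites in addition to the fixed effects for intervention and covariates of interest". That is the only device named for correlation within a patient. The plan does not say whether the patient effect is an intercept alone or also a slope over time. It names no residual covariance structure, robust standard error or small-sample degrees-of-freedom method.

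The difference between arms "will be examined by testing the treatment-by-time interaction effect on each outcome". If the interaction is not significant, the marginal difference is tested in the same model without it. The paragraph also promises visit-specific estimates: "The score changes from baseline to each time point and their difference between TEAM and TECH will be estimated with 95% confidence intervals". Aim 2 reuses these models and reports subgroup intervals of the same kind where heterogeneity is found.

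Compensation for Participation lists self-report measures at baseline, 6 and 12 months. The COVID paragraph treats the 6-month survey as the primary-outcome survey.

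**The concern.** A linear mixed model with a patient random intercept and independent, equal-variance residuals implies compound symmetry. It therefore attaches the same standard error to every change between two visits when data are complete. If the true variance of change differs between baseline-6 and baseline-12 months, no single figure can be right for both.

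At stake are the visit-specific intervals for change and for the TEAM-TECH difference, which readers will use to judge how large the effect is and whether it lasts. An interval labelled 95% could cover appreciably less at one visit and more at another, and nothing in the output would show it.

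**Working it through.** **No figure to reproduce.** The documents give no visit correlation, SD by visit, standard error or interval width. The correlations and SDs below are assumptions.

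**Inputs from the documents.** Three self-report visits (Compensation for Participation); about 252 per arm after 25% attrition (Sample Size and Power Calculations); 95% intervals from the Aim 1 model.

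**Formulas** (random intercept, free treatment-by-visit means, complete data):
- True variance of a change between visits j and k: D(j,k) = SDj² + SDk² − 2·r(j,k)·SDj·SDk.
- The model uses the mean of D over all visit pairs, M, for every change.
- SE ratio, model to true: √(M/D).
- Coverage = 2Φ(1.96 × SE ratio) − 1.

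**Example, correlations .7/.5/.7, all SDs 1.** D(0,6) = 2(1 − .7) = 0.6; D(0,12) = 2(1 − .5) = 1.0; D(6,12) = 0.6. M = 2.2/3 = 0.733.
- 12 months: √(0.733/1.0) = 0.856; coverage 2Φ(1.678) − 1 = 90.7%.
- 6 months: √(0.733/0.6) = 1.106; coverage 2Φ(2.167) − 1 = 97.0%.

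**Range of patterns** (correlations in the order baseline-6, baseline-12, 6-12 months):

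| Correlations | SDs at 0/6/12 | SE ratio, 6 mo | Coverage, 6 mo | SE ratio, 12 mo | Coverage, 12 mo |
|---|---|---|---|---|---|
| .7/.5/.7 | 1/1/1 | 1.106 | 97.0% | 0.856 | 90.7% |
| .6/.4/.6 | 1/1/1 | 1.080 | 96.6% | 0.882 | 91.6% |
| .6/.45/.6 | 1/1/1 | 1.061 | 96.2% | 0.905 | 92.4% |
| .5/.5/.7 | 1/1/1 | 0.931 | 93.2% | 0.931 | 93.2% |
| .5/.5/.5 | 1/1/1 | 1.000 | 95.0% | 1.000 | 95.0% |
| .5/.5/.5 | 1/1.2/1.2 | 1.027 | 95.6% | 1.027 | 95.6% |
| .5/.5/.5 | 1/1.2/1 | 0.967 | 94.2% | 1.077 | 96.5% |

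**Width.** With 252 per arm and correlations .7/.5/.7, the half-width for the TEAM-TECH difference in 12-month change should be 1.96·√(2 × 1.0/252) = 0.175 SD. The random-intercept model reports 1.96·√(2 × 0.733/252) = 0.150 SD.

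**Simulation.** With complete data, 252 per arm and no true difference, .7/.5/.7 gave intervals excluding zero in 9.9% of trials at 12 months and 2.9% at 6 months. The formula gives 9.3% and 3.0%. A smaller simulation with 337 per arm and 25% missing at 12 months used first-order autoregressive decay, with 6-month correlations of 0.5 and 0.7. It gave 12-month coverage of 91.4% and 92.0%. With 800 runs its Monte Carlo error is about √(.05 × .95/800) = 0.8 percentage points at 95% coverage (its compound-symmetric check returned 93.2%), so it supports the pattern but not the decimals.

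**Joint test.** The treatment-by-time Wald test has type I error of 5.0-5.7% across the three-visit patterns.

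**Possible fourth visit.** The 6-month visit is labelled Timepoint 3, so an undescribed visit may exist. If one is assumed at 3 months, with 6-month correlations of 0.5 to 0.8 and autoregressive decay, 12-month coverage is 88.9-86.5%, 6-month coverage is close to 95%, and the joint test reaches at most 6.8%.

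**The case against.** The strongest reply has four parts.

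1. **The text does not say intercept only.** Correct: a random slope would let variance and correlation change with time. The plan would then have to say so. Until it does, the intervals rest on an unstated choice.

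2. **The direction is not established.** Correct. Coverage is exact under compound symmetry, and the 12-month interval is too wide with SDs 1/1.2/1. Undercoverage at 12 months in the main scenarios comes from correlation that falls with time, which is plausible but not documented. Under that decay the 6-month interval, at the visit tied to the primary outcomes, is too wide; the cost there is precision.

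3. **The planned tests hold up.** Largely correct. The joint test stays near 5%, and with complete, balanced data the marginal comparison is between patients and valid under any within-patient covariance. The intervals are still promised results.

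4. **Diagnostics are planned.** The plan examines distributions over time and allows labelled departures. Unequal variances might be noticed, but there is no rule for the covariance, and a later correction would have to be reported as a deviation.

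The argument also does not carry over to categorical utilization, where a random intercept does not impose equal marginal variances.

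**Conclusion.** The point holds as a conditional one. For continuous outcomes, and if the patient effect is a random intercept, the visit-specific intervals have 95% coverage only when the variance of change is the same for all visit pairs, or happens to match their average. Under the assumed decay (.6/.45/.6 to .7/.5/.7), coverage is about 91-92% at 12 months and 96-97% at 6 months. The joint treatment-by-time test is little affected.

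Three stronger readings are tempting, and the documents do not support them.
- **That the PHQ-4 entry threshold makes the 12-month interval too narrow.** Selection does shrink baseline variance and its correlation with follow-up. Applied alone to a compound-symmetric population, however, it left coverage slightly above 95% (95.3-95.8%).
- **That the plan will declare a 12-month difference too easily.** No visit-specific significance test is planned. The 9.9% figure describes the interval used as a test, which the plan does not list.
- **That Aim 2.a needs a separate covariance for active and inactive disease.** The cut on HBI or UCAI limits those scores at baseline, but the outcome highlighted for Aim 2.a is behavioral health severity, which it does not limit.

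**What to change.** For continuous outcomes, replace the patient random intercept with an unstructured covariance over the visits, using Kenward-Roger degrees of freedom. Alternatively, keep the patient random effect and use robust standard errors clustered on patient. Name in advance the simpler structure to be used if the unstructured model does not converge. Use the same specification for the Aim 2 subgroup intervals. For categorical utilization, state the random-effect terms; the unstructured residual covariance is not meant for it.

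The cost is a change of SAP wording and a few more parameters: with three visits 3 × 4/2 = 6 instead of two, and with four visits 4 × 5/2 = 10. About 505 participants can support either. If compound symmetry is true, interval widths are essentially unchanged.

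### The main Aim 1 contrast leaves each randomized arm its own baseline mean and does not adjust for the baseline score, so it is probably less precise than it need be

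*Combined protocol and SAP*

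**What the plan says.** Under Quantitative Analysis, Aim 1 uses generalized linear mixed models with fixed effects for intervention and for covariates that are not named there, and random effects for patients and sites. The first test is the interaction: "the null hypothesis of homogeneous change in outcomes overtime between TEAM and TECH will be examined by testing the treatment-by-time interaction effect". The reported effect follows the same logic: "The score changes from baseline to each time point and their difference between TEAM and TECH will be estimated with 95% confidence intervals". Baseline is therefore one of the modelled outcome visits.

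If the interaction is not significant, the plan tests a marginal arm difference from the same model without it. The error rate is set by "All hypothesis tests for Aim 1 will be conducted at the overall significance level of 0.05".

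Nowhere does the plan say that the baseline value of the outcome is a covariate, or that the arms share one baseline mean. The Covariates section does not list the baseline outcome score. The baseline analysis that precedes hypothesis testing looks for differences between arms but prescribes no adjustment. The COVID paragraph adds an indicator of COVID confounding to the primary analysis. Aim 2 reuses the Aim 1 models with higher-order interactions.

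**The concern.** A model with an intervention main effect plus treatment-by-time estimates a separate baseline mean in each arm. With complete data its contrast is the arm difference in mean change. Patients are individually randomized, so the true baseline means are equal, and any observed baseline gap is chance. The change contrast subtracts that gap in full. Baseline adjustment subtracts only the part that predicts follow-up.

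Precision is scarce here. The pilot figures are "TECH (n=73; ES .49) versus TEAM (n=106; ES .36) for the behavioral composite", a gap of 0.13, and 0.22 against 0.16 on the biological composite, a gap of 0.06. Avoidable variance widens every reported TEAM-TECH interval and carries into the smaller Aim 2 subgroups. Randomization is stratified by age, disease activity and IBD type but not by PHQ-ADS, so the design does not directly limit chance imbalance on the behavioral primary outcome.

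**Working it through.** **Inputs from the documents.** Enrolment of 675, "with approximately 337 participants enrolled into both TEAM and TECH"; two Aim 1 tests and 25% attrition; overall level 0.05; two-sided Wald tests; pilot effect sizes as above. Self-report visits at baseline, 6 and 12 months are taken from the Compensation section.

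**Assumptions.** Level 0.025 per test (Bonferroni for two tests). The correlations, the ratio k = baseline SD / follow-up SD, and the dropout split are also assumed: 15% lost before 6 months and 12% of the remainder before 12 months, so 1 − 0.85 × 0.88 = 25.2% in all.

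**The plan's own power figure.** Allowing for both tests and the expected losses, the plan claims: "a sample size of 505 (approximately 252 per treatment group) will provide over 99.9% power for the hypothesis test for Aim 1".
- 675 × 0.75 = 506, against 505.
- Within-arm change, ES 0.36, n = 252: Φ(0.36 × √252 − 2.241) = Φ(3.47) = 99.97%. ES 0.49 gives more than 99.99%. The stated figure reproduces for behavioral change within an arm.
- It also reproduces if 0.49 is read as a between-arm effect (99.94%).
- For a between-arm gap of 0.13 with unit SD: 0.13 / √(2/252) = 1.46, and Φ(1.46 − 2.241) = 21.7%.

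The stated power therefore does not show that the TEAM-TECH contrast has precision to spare.

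**One follow-up, complete data.** Set the follow-up SD to 1, the baseline SD to k and the correlation to r.
- Change-score variance is proportional to 1 + k² − 2rk.
- Baseline-adjusted variance is proportional to 1 − r².
- The difference is (k − r)², which is never negative and is zero only when r = k.
- With k = 1 the ratio is (1 + r)/2, a loss of (1 − r)/2: 35%, 25%, 20% and 15% for r = 0.3, 0.5, 0.6 and 0.7.
- With k = 0.8 and r = 0.5 the ratio is 0.75 / 0.84 = 0.893, a loss of 11%.

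**Three visits with dropout.** Exact generalized least squares, 337 per arm, comparing a common baseline mean with separate baseline means. Entries are the reduction in variance of the 6-month contrast, with the variance ratio in brackets.

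| Correlations 0–6, 0–12, 6–12 | k = 1 | k = 0.8 |
|---|---|---|
| 0.3, 0.25, 0.5 | 31% (0.686) | 19% (0.811) |
| 0.5, 0.4, 0.6 | 22% (0.779) | 9% (0.907) |
| 0.6, 0.5, 0.7 | 18% (0.825) | 5% (0.950) |
| 0.7, 0.6, 0.75 | 13% (0.870) | 2% (0.984) |

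At 12 months with k = 1, the first three ratios are 0.685, 0.752 and 0.794.

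**Power of the single 6-month contrast**, second row, k = 1, difference 0.13 SD, level 0.025. The standard error falls from 0.0820 to 0.0724.
- Separate baselines: Φ(0.13/0.0820 − 2.241) = Φ(−0.66) = 0.26.
- Common baseline: Φ(0.13/0.0724 − 2.241) = Φ(−0.45) = 0.33.

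This treats the pilot gap as a difference in outcome SDs, which the documents do not confirm.

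**The case against.** The strongest reply is that the plan is silent rather than opposed. It gives no model equation, leaves the covariate list open and says covariates will be fixed in advance, so calling the contrast raw would go too far. That stands as to wording. It does not remove the point. Covariates that are constant within a patient, such as COVID status, largely cancel from a change contrast unless they interact with time. If baseline adjustment is intended, the plan has to say so.

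The second reply is about size. A reader might infer a fixed loss of roughly 18% to 31%, or that change scores always lose whenever r is below 1. The documents support neither. That range needs equal SDs and correlations no higher than 0.6, and the loss vanishes when r = k. Entry requires PHQ-4 of at least 6, and PHQ-ADS is also a depression and anxiety score, so selection could narrow the baseline spread and put k below 1. This stands, and is why both columns are shown.

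Third, the power figures describe one 6-month contrast, not the plan's interaction test followed by a marginal test. A larger gain can be shown at 0.20 SD (0.58 to 0.70 at r = 0.5, k = 1), but the documents name no such difference. At 0.13 SD power is low either way.

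Fourth, chance imbalance on the IBD outcome is already limited, because randomization is stratified by active or inactive disease and the activity indices feed that composite. This also stands.

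**Conclusion.** The point holds as a matter of efficiency. As written, the main Aim 1 test and the reported change differences let each arm keep its own baseline mean and make no use of the baseline score as a predictor. A reader might infer that the estimate is biased or the test invalid. Neither follows: under randomization the change contrast is unbiased, and it answers the question that the plan asks.

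The avoidable variance at 6 months is about 13% to 31% under equal SDs, and about 2% to 19% if the baseline SD is 0.8 of the follow-up SD, for r(0,6) from 0.7 down to 0.3. All of these rest on assumed correlations, SD ratio and dropout split. The direction does not depend on them: adjustment never does worse in the comparison above. The fallback marginal test is a different quantity and lies outside these figures. The change should be made because it costs almost nothing, not because the present plan is wrong.

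**What to change.** State in the SAP that the longitudinal model for each continuous outcome has one baseline mean common to both arms, with time effects and treatment-by-time terms at post-baseline visits only. Test those post-baseline treatment terms, and report the adjusted TEAM-TECH differences at 6 and 12 months with 95% confidence intervals. Use the same structure for Aim 2.

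This form keeps participants who have only a baseline score, in line with the intent-to-treat statement. The alternative, modelling only the 6- and 12-month scores with baseline and its interaction with time as covariates, would recover similar precision but drop those participants.

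The cost is one SAP sentence and one model statement, using data already collected. It should be settled while the statistician is still masked, since the plan's own rule would label a later change as a deviation.
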